## Results for primary outcomes

Effect of Naltrexone on Neural Activity to Messages task: To examine the effect of naltrexone on neural activity to the social warmth task, analyses were constrained to the a-priori defined VS and MI mask. VS and MI activity was greater to messages from close others than strangers (*left*  $t(76)=6.138$ ,  $p < .001$ ; *right*  $t(76)=4.493$ ,  $p < .001$ ). Naltrexone, however, reduced VS and MI activity to the social warmth task as compared to placebo (*left*  $t(75)=1.859$ ,  $p=.034$ ; *right*  $t(75)=2.198$ ,  $p=.016$ ).

Effect of Naltrexone on Feelings of Social Connection to Messages task: The effect of drug on feelings of social connection to the messages task was in the expected direction, but did not reach statistical significance ( $p > .10$ ).

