(vs. neutral messages) from close friends and family members activates the ventral striatum (VS), ventral tegmental area (VTA), pregenual (pACC) and dorsal anterior cingulate cortex (dACC); orbitofrontal cortex (OFC), and insula (Inagaki & Eisenberger, 2013), all regions known to be high in  $\mu$ -opioid receptors (Cross, Hille, & Slater, 1987; Jones et al., 1999; Panskepp & Bishop, 1981; Vanderschuren, Stein, Wiegant, & Van Ree, 1995; Willoch et al., 1999; Wise & Herkenham, 1982; Zubieta et al., 2001). Similarly, the VS, OFC, and VTA are more active when viewing images of close others (vs. strangers or acquaintances) such as one's own baby or romantic partner (Acevedo, Aron, Fisher, & Brown, 2012; Bartels & Zeki, 2004; Strathearn, Li, Fonagy, & Montague, 2008). Though not tested yet, it is possible that opioid antagonism may reduce activity in these affiliation-related neural regions.

Together, emerging evidence from humans and animals point to the possibility that  $\mu$ -opioids contribute to the experience of bonding and connecting with others, but few have explored the role of opioids in social bonding in humans. As such, the current study aims to test the brain opioid theory of social attachment to better understand the role of opioids in maintaining close social bonds.

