To assess between-group differences in the effect of naltrexone vs. placebo on neural responses to the different tasks, we will conduct two kinds of analyses for each task. First, based on a priori hypotheses regarding the effect of naltrexone on affiliation-related neural responses, we will conduct region-of-interest (ROI) analyses, using structurally-defined ROIs, to examine between-group differences in neural activity in these pre-specified neural regions ( $p < .05$ , corrected). For the task where participants read messages from their loved ones, ROIs of the VS and mid-insula, have been created (with the PickAtlas toolbox) using the automated anatomical atlas (AAL; Tzourio-Mazoyer et al., 2002), and will be examined to see if average neural activity in these regions differs between naltrexone and placebo participants in response to the messages. Similarly, for the picture-viewing task, ROIs of the left and right VS will be analyzed in the same way (these have also been structurally defined previously; Inagaki et al., 2015). Second, to more fully investigate the specific neural regions that are differentially activated as a function of naltrexone (beyond the predicted ROIs), we will conduct whole-brain between-group analyses to see which neural regions differ in activity among participants exposed to naltrexone vs. placebo ( $p < .001$ , 10 voxels).

Feelings of social connection: To assess between-group differences in the effect of naltrexone vs. placebo on self-reported feelings of connection in response to the scanner tasks, we will conduct independent samples t-tests.

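### The printed p-values for the naltrexone effect on VS and MI activity are one-sided without saying so; two-sided, the left-hemisphere effect does not pass .05 and the right passes only if no correction is applied across hemispheres

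*Combined protocol and SAP*

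**What the plan says.** Statistical Considerations names neural activity as a primary outcome, alongside self-reported feelings of connection. The ROI analyses are introduced as "based on a priori hypotheses regarding the effect of naltrexone on affiliation-related neural responses", and between-group differences are to be examined "in these pre-specified neural regions ( $p < .05$ , corrected"). For the messages task, the ventral striatum (VS) and mid-insula (MI) regions "will be examined to see if average neural activity in these regions differs between naltrexone and placebo participants in response to the messages". The section names neither a tail nor a correction method. The exploratory whole-brain comparison has its own threshold, p < .001 with 10 voxels.

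A direction appears, tentatively, at the end of Scientific Background: "it is possible that opioid antagonism may reduce activity in these affiliation-related neural regions".

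Results for primary outcomes gives the drug effect as left t(75)=1.859, p=.034 and right t(75)=2.198, p=.016, and concludes: "Naltrexone, however, reduced VS and MI activity to the social warmth task as compared to placebo". No tail is stated beside the p-values, and no correction is mentioned.

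**The concern.** A p-value printed without a tail, for a question about whether two arms differ, will be read as two-sided. These two are about half the two-sided values. A one-sided test at .05 allows an error rate of .05 in the claimed direction, where a two-sided .05 test allows .025.

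The ROI result on the messages task is the only positive drug effect in the document. The self-report result for the same task is given as non-significant (p > .10). The sentence claims a reduction in both hemispheres, so the choice of tail decides whether half of that claim stands. The plan's threshold is also a corrected one, and the results do not show that any correction was made.

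**Working it through.** **Inputs** (all from Results for primary outcomes)
- Left: t = 1.859, df = 75, printed p = .034.
- Right: t = 2.198, df = 75, printed p = .016.
- The degrees of freedom are coherent: the within-person contrast has df 76, so 76 + 1 = 77 participants; the two-group contrast has df 75, so 75 + 2 = 77.

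**Step 1: reproduce the printed figures.** One-sided p = P(T > t) with 75 df.
- Left: P(T > 1.859) = .0335. Allowing for rounding of t (1.8585 to 1.8595), the range is .03351 to .03344, so the printed .034 agrees to rounding.
- Right: P(T > 2.198) = .0155, printed as .016.

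**Step 2: two-sided values.** p = 2 × P(T > |t|).
- Left: 2 × .03347 = .0669.
- Right: 2 × .01552 = .0310.

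Rounding of t cannot bring .067 to .034 or .031 to .016. Changing df between 70 and 76 does not help either: two-sided left stays at about .067 and right at about .031. A normal approximation gives .063 and .028 two-sided. Both hemispheres fit one tail, so an isolated typing error is unlikely.

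**Step 3: compare with critical values at 75 df.**

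| Test | Critical t | Left 1.859 | Right 2.198 |
|---|---|---|---|
| One-sided .05 | 1.665 | passes | passes |
| Two-sided .05 | 1.992 | fails | passes |
| Two-sided .05, Bonferroni over 2 | 2.287 | fails | fails |

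**Step 4: the effect of a correction.** The method is not stated. Assuming Bonferroni over the two hemispheres (multiply p by 2):
- One-sided: left 2 × .0335 = .067; right 2 × .0155 = .031.
- Two-sided: left 2 × .0669 = .134; right 2 × .0310 = .062.

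On that assumption the left result fails even if a one-sided test is granted.

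**Step 5: approximate effect size.** Arm sizes are not given. Assuming 38 and 39 (total 77), d = t × √(1/38 + 1/39) = t × 0.2279, with intervals from the noncentral t:
- Left: d = 0.42 (95% CI −0.03 to 0.87).
- Right: d = 0.50 (95% CI 0.05 to 0.95).

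The two estimates are close. The left interval includes zero and the right one only just excludes it.

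**The case against.** The best defence is that a direction was expected. Scientific Background reports earlier work in which naltrexone lowered feelings of connection and suggests that antagonism may reduce activity in these regions. Statistical Considerations refers to a priori hypotheses and to predicted ROIs. Words such as differs are ordinary usage and do not formally declare a two-sided test. If a one-sided test was fixed before the data were seen, its total nominal error rate is still .05.

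Part of this stands. The plan never says two-sided, so a reader who infers that the results broke a declared two-sided rule goes further than the text allows. The left effect is non-significant on a two-sided test, not under every test the plan could be read to permit. But an expected direction is not a pre-specified one-sided test. The Background wording is tentative, the a priori hypotheses are given no direction where the test is described, and nothing shows that the tail was fixed in advance. Even if a one-sided test was intended, it had to be labelled beside the p-values.

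Three other stronger readings are not supported:
- That the right-hemisphere result is secure at .031. The plan asks for a corrected p, and whether .031 survives depends on a method the document does not give.
- That the self-report result shares the fault. Nothing shows the tail behind p > .10, and doubling a one-sided p there could not change a non-significant conclusion.
- That there is no left-hemisphere effect. The interval in the working is compatible with a sizeable one; the point is that the claim does not pass a two-sided test.

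**Conclusion.** The concern holds. That the printed p-values are one-sided follows from the printed t and df with no further assumption, and no one-sided test is declared anywhere in the document. Two-sided, they are .067 (left) and .031 (right) against a critical t of 1.992. The claimed reduction in the left hemisphere therefore fails a two-sided .05 test, and the right passes before correction.

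How far the right-hemisphere claim survives the plan's own threshold cannot be settled from the document. Under the assumed Bonferroni correction over two hemispheres it would not survive two-sided (.062), and the left would fail on either tail (.067 one-sided, .134 two-sided). The statistics need no new data to correct, but the conclusion on a primary outcome changes.

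**What to change.** In Results for primary outcomes:
- State that the printed values are one-sided and that the plan did not specify this.
- Report two-sided p = .067 (left) and .031 (right), with mean differences and 95% confidence intervals.
- State which correction the plan meant, over which tests, and whether it was applied; give the corrected values.
- Limit the claim of a reduction to what passes. Withdraw it for the left hemisphere, and keep it for the right only as far as the stated correction allows.

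If a statement on sidedness is added to Statistical Considerations, it should cover the ROI and self-report tests only and leave the whole-brain threshold of p < .001 with 10 voxels as it is. It should be dated and marked as a clarification made after the results were known, so that it is not taken for pre-specification.

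The work is a short revision of the results paragraph using the existing data, plus the dated note. The price is a less favourable p-value and a narrower claim.
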